## FUNDING AND SUPPORT

Funder	Type of Financial or Non-Financial Support
Methusalem funding	Financial Support

Reasonable time investment and travel expenses incurred by Trial participants and directly related to participation in the Trial, will be reimbursed by the Sponsor, as follows:

- (i) At a flat rate of € 950  
When the subject does not complete the study, but terminates the study earlier, the compensation will be calculated as follow:
  - Stop at the end of visit 2: € 225
  - At the end of visit 4: € 575
  - At the end of visit 6: € 950
- (ii) If the subject require contraception to take part in this study, the subject will be reimbursed for the actual cost incurred.

A reimbursement payment log will be kept by the Investigator Site staff and made available for monitoring and verification purposes.

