## TRIAL FLOWCHART

### Schedule of Events – Trial specific Procedures / Assessments

Please indicate in the flowchart with different colors whether a procedure is performed as part of the standard of care or specifically for the Trial.  
Describe the visits and applicable procedures/investigations (with a reference number or letter) in more detail in a footnote below the Trial flowchart

Procedures/ Assessment	Screening	Rando- misation	Treatment Period				
			Visit 0	Visit 1	Visit 2	Visit 3	Visit 4
Visits / Contacts			0	0	0	3	3
Timing (weeks)	-30 Days to -1	-30 Days to -1	day -7 to 0	day -7 to 0	day 17 to 21	day 17 to 21	day 66 to 70
Visit Window (days)							
Informed consent	X 						
Inclusion / Exclusion criteria	X						
Demographics	X						
Medical, Surgical history	X						
Physical examination	X						
Weight / Height	X						
Vital Signs	X						
Pregnancy Test	X						
Urinalysis							
Randomisation	X						
Study drug administration 				X	X	X	X
Migrating motor complex measurement 			X		X		X
Intragastric pressure measurement 			X		X		X
Blood collection 	X			X		X	X
Duodenal aspirates 	X			X		X	X
Patient Reported Outcomes (PRO) I (questionnaire) 							
Endoscopy 				X		X	X
Duodenal biopsy 				X		X	X
Diary				X		X	X
Stool specimens 				X		X	X
(Serious) Adverse event (S/AE) assessment				X		X	X
Concomitant Medication (CM)	X	X	X	X	X	X	X

1 Enrollment and screening questionnaires: the following questionnaires will be used for screening: Patient Health Questionnaire, Dutch version of Rome IV criteria questionnaire for functional GI disorders. Enrollment and screening will be done via an online system (Quatrics).

2 Study drug administration: assignment of treatment (placebo and obeticholic acid) will be randomized before study visit 1. Either placebo or obeticholic acid will be administered orally in a single-blind fashion for 21 days. After a washout period of 28 days, either placebo or obeticholic acid will be administered as appropriate for an additional 21 days.

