### 5.1 Investigational Medicinal Product and Dosing Regimen

In this study, participants will receive in total one dose of OCA (OCALIVA®, Intercept Pharmaceuticals, New York, United States) and one dose of placebo (Intercept Pharmaceuticals, New York, United States) in a phase II, single-blind, randomized crossover fashion.

One dose of study medication consists of 1 tablet (10mg) of placebo or OCA. OCA and placebo will be orally administered with water in the morning for 21 days after the examinations at preintervention.

OCALIVA® is a drug which is only available on prescription, it is indicated for the treatment of primary biliary cholangitis (ATC code A05AA04). OCALIVA® tablets contain 10 mg obeticholic acid and 176 mg Microcrystalline cellulose, 12 mg Sodium starch glycolate, 2 mg Magnesium stearate, tablets are film coated and dissolve in the acidic environment of the stomach. One dose of study medication will contain 10 mg obeticholic acid.

Placebo tablets will be obtained from Intercept Pharmaceuticals, New York, United States and will contain 320 mg lactose monohydrate, 10 mg carmellose sodium, 70 mg corn starch, 55 mg cellulose microcrystalline, 20 mg silicium dioxide anhydrous and 13 mg magnesium stearate per tablet.

Administered medications will be properly registered in KWS system.

Participants will take each OCA and placebo for 21 days across washout period at home. Drug compliance will be monitored with a daily questionnaire and subjects will state the time of taking the medication. When participant forgets to take dose at regular time, participant can still take drug until 12 hours to next dose. The bottles with the tablets will be collected after the end of each treatment period and the number of tablets will be counted and registered. With regard to medication compliance, it is not considered a deviation if the rate of taking study medication is more than 80%.

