## 5.2 Drug Accountability

Participants will take medication home. The investigators will prepare blinded containers which contain the study medication to assure single blinding. Therefore, each subject's medication kit will be labelled as following:

Seulement pour les études cliniques	Alleen voor klinische studies	Nur für klinische Studien
Numéro de protocole: OCARINA Numéro EudraCT: 2020-004180-13	Protocolnummer: OCARINA EudraCT-Nummer: 2020-004180-13	Protokollnummer: OCARINA EudraCT Nummer: 2020-004180-13
Contenu: Acide obéticholique 10 mg ou placebo Conditions de stockage: 20-25°C Posologie: 1 comprimé une fois par jour le matin Utilisation orale Numéro d'identification: XX Numéro de personnage: XXXXXXXX Date d'expiration: MM / DD / YYYY	Inhoud: Obeticholzuur 10 mg of placebo Opslag condities: 20-25°C Dosering: 1 tablet 1 keer per dag in de ochtend Oral gebruik ID nummer: XX Chargenumber: XXXXXXXX Vervaldatum: MM / DD / YYYY	Inhalt: Obeticholsäure 10 mg oder Placebo Lagerbedingungen: 20-25°C Dosierung: 1 Tablette einmal täglich morgens Oraler Gebrauch ID Nummer: XX Chargenumber: XXXXXXXX Ablaufdatum: MM / DD / YYYY
Docteur: [name] [name], University of Leuven, UZ Gasthuisberg, Belgium, [contact]	Dokter: [name] [name], University of Leuven, UZ Gasthuisberg, Belgium, [contact]	Doktor: [name] [name], University of Leuven, UZ Gasthuisberg, Belgium, [contact]
Tenir hors de la portée et de la vue des enfants	Buiten het bereik en zicht van kinderen houden	Darf nicht in die Hände von Kindern gelangen

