## 5.3 Concomitant / Prohibited Medication / Treatment

The following drugs must not be used 2 weeks before, during and 1 week after the study

- Drugs that can affect gastrointestinal function, motility or sensitivity or gastric acidity.
- Centrally acting medication, including antidepressants, antipsychotics and/or benzodiazepines
- Warfarin
- Proton pump inhibitors

If these drugs are taken during study medication, IMP medication will be discontinued and the subject will be excluded from the study at that time. Study data up to the time of exclusion will be available.

If these drugs are taken during the washout period, a period of at least 2 weeks should be allowed before starting the second medication.

The following drugs must not be used 1 year before, during and 1 week after the study

- Centrally acting medication, including antidepressants, antipsychotics and/or benzodiazepines (in the last year before screening visit).

If these drugs are taken during study medication, IMP medication will be discontinued and the subject will be excluded from the study at that time. Study data up to the time of exclusion will be available.

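### The legible schedule describes no medication question before period 2 to trigger the 5.3 washout rule, and period-2 stool days and the final visit window are not tied to the actual second start

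*Combined protocol and SAP*

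**What the plan says.** **The rule.** Section 5.3 lists drugs that are barred around and during the study and adds, for the interval between treatments: "If these drugs are taken during the washout period, a period of at least 2 weeks should be allowed before starting the second medication". Use during study medication is handled differently: treatment stops and the participant is excluded.

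**The calendar.** Trial Flowchart footnote 2 gives 21 days of the first treatment and continues: "After a washout period of 28 days, either placebo or obeticholic acid will be administered as appropriate for an additional 21 days". After screening and randomisation, the visit windows that can be read are day -7 to 0, day 17 to 21 and day 66 to 70. Concomitant medication is a row of that visit table. Funding and Support sets payment steps at the end of visits 2 and 4 and finally "At the end of visit 6".

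**Contacts outside the visit table.** Section 5.2 says "Participants will take medication home". Section 5.1 says "The bottles with the tablets will be collected after the end of each treatment period", for a tablet count. It also says "Drug compliance will be monitored with a daily questionnaire and subjects will state the time of taking the medication", and it places dosing "for 21 days after the examinations at preintervention". Footnote 8 has stool samples brought back within 2 weeks. Section 6.7 has safety events asked about at every contact.

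**Stool days.** Footnote 8 puts the pre-dose sample at day 0 for intervention 1 and day 28 for intervention 2. Later samples are on days 2, 4, 7, 14 and 21, and on days 30, 32, 35, 42 and 49.

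**The concern.** The 5.3 condition can be applied only if the site learns of the drug use before the first period-2 tablet. The participant takes that tablet at home, and the legible plan describes no question about medication close to it. A site could therefore start the second treatment against 5.3 without knowing.

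The second issue is what happens when the condition is applied. It delays period 2, but the stool days and the final visit window are written as fixed study days. Footnote 8's stool days also disagree with the washout that footnote 2 describes. At stake are the stool microbiota data, which belong to a secondary endpoint, and, after a delay, the length of treatment before the final tests. Those tests include the hunger scores that form the primary endpoint.

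**Working it through.** **Inputs.** Treatment period 21 days and washout 28 days (footnote 2); visit windows day 17 to 21 and day 66 to 70 (flowchart); clear interval 14 days (5.3); stool days (footnote 8).

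**1. Reproduce the plan's own window.** Period-2 start = 21 + 28 = day 49. Treatment days 17 to 21 of period 2 = 49 + 17 to 49 + 21 = day 66 to 70. This matches the flowchart. If tablets are counted from day 1, the first period-2 tablet is on day 50 and days 66 to 70 are dosing days 17 to 21. The match therefore supports a start at about day 49 but does not fix it to the day. Day 49 is used below.

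**2. When 5.3 calls for a delay.** 49 - 14 = 35, so use up to day 35 already leaves 2 weeks. For use on days 36 to 48:
- last use on day 36: earliest start 36 + 14 = day 50, a delay of 1 day;
- last use on day 48: earliest start 48 + 14 = day 62, a delay of 13 days.

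**3. Is there a described trigger?** The first legible medication check after day 21 is at day 66 to 70, which is 66 - 49 = 17 to 70 - 49 = 21 days after period 2 begins. The other contacts compare as follows:
- Bottle collection has no date and is described for a tablet count.
- Second-kit hand-over is implied by 5.1 and 5.2 and has no date or medication question.
- If return is within 2 weeks of collection, the day-21 stool sample is due by 21 + 14 = day 35, before days 36 to 48.
- The daily questionnaire is described for compliance and time of intake only.
- Section 6.7 attaches a safety question to contacts, not a medication question.

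**4. Effect if use ends by day 48 and no delay is made.** The gap to the final measurements is 66 - 48 = 18 days at the shortest and, for use on day 36, 70 - 36 = 34 days at the longest. All exceed 14 days. Counted from day 49, the stool days would be 49, 51, 53, 56, 63 and 70. The day-63 sample is at least 63 - 48 = 15 days after use, so only samples before it could lie within 2 weeks of use.

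**5. Footnote 8 against footnote 2.** Intervention-2 sample days less 28: 0, 2, 4, 7, 14, 21, the same spacing as in period 1. Under footnote 2 the washout runs from day 21 to day 49. Five of the six samples (days 28, 30, 32, 35, 42) fall inside it and the sixth falls on the day period 2 starts. If day 28 were the true start, washout would be 28 - 21 = 7 days and the final window would be 28 + 17 to 28 + 21 = day 45 to 49, not day 66 to 70.

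**6. Fixed final window after a delay.**
- Delay of 1 day (start day 50): 66 - 50 to 70 - 50 = treatment days 16 to 20.
- Delay of 13 days (start day 62): 66 - 62 to 70 - 62 = treatment days 4 to 8.

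**The case against.** **The gap is inferred from a damaged table.** Payment refers to a visit 6, but only five windows after screening and randomisation survive in the text, so at least one column is lost. The medication row is marked at every surviving window and cannot show where it is unmarked. Payment steps at visits 2, 4 and 6 fit three pairs of visits, but an unpaid call would not appear there. This stands, and the point is limited to what can be read.

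**Contact before period 2 is implied.** A second kit has to reach the participant, and 5.1 mentions examinations before dosing. A reader might still infer that nobody sees or speaks to the participant before the second treatment. The documents do not support that. Section 7.2 reuses the first pre-treatment endoscopy and motility data for the second part, which suggests that those tests are not repeated, but it does not exclude a dispensing contact. The diary's content is not given either. What remains is a hand-over without a date or a medication question.

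**The rule is worded as advice.** For the 2-week interval 5.3 says should, where the prohibition itself says must. That is fair, but a recommended interval also needs someone to know that it applies.

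**The stool consequence uses a borrowed criterion.** Section 5.3 governs when treatment starts and sets no validity rule for samples. For that reason no count of affected samples is claimed.

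**Footnote 8 may be counted from another origin.** Counted from the end of period 1, its days become 21 + 28 = 49 to 21 + 49 = 70, which is consistent with footnote 2. This may well be what was meant. The footnote does not say so, and it counts intervention 1 from its own start.

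**A site would move the final visits after a delay.** Probably, but no rule says so, and 9.4 does not permit planned deviations.

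**Conclusion.** This is a minor to moderate operational finding in two parts.

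The firmer part is timing. As written, footnote 8 places the period-2 stool samples in the washout, and the day 66 to 70 window is not linked to the actual second start. Taken literally, a 13-day delay would put the final tests at treatment days 4 to 8 instead of 17 to 21.

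The second part is that the 5.3 interval has no described trigger in the legible schedule. The effect on results is limited. A reader might infer that the primary hunger comparison is compromised by undetected washout use. For use ending by day 48 the documents do not support that, since those scores come at least 18 days later. Only some early period-2 stool samples of an affected participant could be touched. Use that runs on into period 2 falls under the separate 5.3 rule of stopping treatment and excluding the participant.

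The conclusion assumes a start at about day 49 and that no lost column holds a contact between day 21 and day 66. The protocol gives no rate of prohibited-drug use, so the expected number of affected participants cannot be stated. No sample size, power or error-rate figure changes.

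**What to change.** 1. In footnote 8 and the flowchart, count the period-2 stool days (0, 2, 4, 7, 14, 21) and the final visit window (days 17 to 21) from the actual first period-2 tablet. With an undelayed start this gives stool days 49 to 70 and leaves the window at day 66 to 70.
2. Date the second-kit hand-over just before period 2, or add one short call by existing staff at that point. Ask about listed drugs in the previous 14 days, adverse events, and pregnancy or intention of pregnancy (both listed in 4.5).
3. State in 5.3 that period 2 starts only after this check and at least 14 days after the last use of a listed drug.

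The cost is wording in the flowchart, footnote 8 and 5.3, plus about 12 short calls (one per enrolled participant), or none extra if the check is done at hand-over. A delay of 1 to 13 days, which 5.3 already provides for, would occasionally mean rebooking the final manometry and endoscopy. The check relies on self-report: it prompts disclosure but does not verify it.

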## 5.4 Rescue Medication

None

# 6 Safety

## Definitions

### 6.1 Adverse Event (AE)

An AE is any untoward medical occurrence in a patient, clinical investigation participant or participant of the treated group during an experiment who had been administered a pharmaceutical product, and which does not necessarily have a causal relationship with this treatment.

An AE can therefore be any unfavourable and unintended sign (including an abnormal laboratory finding), symptom or disease temporally associated with the use of a medicinal (investigational) product, whether or not considered to be related to the product. Any worsening (i.e. any clinically significant adverse change) in the frequency or intensity of a pre-existing condition, should be considered an AE.

### 6.2 Adverse Reaction (AR)

An AR is any untoward and unintended response to an investigational medicinal product or to an experiment and, when an investigational product is concerned, related to any dose administered. This means that a causal relationship between a medicinal product and an adverse event is at least a reasonable possibility, i.e. the relationship cannot be ruled out.

### 6.3 Serious Adverse Event (SAE)

A SAE is any untoward medical occurrence that at any dose, results in any of the following:

- Death
- A life-threateninga experience
- In-patient hospitalisation or prolongation of existing hospitalisation
- A persistent or significant disability or incapacity
- A congenital anomaly or birth defect
- Important medical events that may be considered an SAE when - based on appropriate medical judgement - they could jeopardise the participant's safety and may require medical or surgical intervention to prevent one of the above outcomes

a The term "life threatening" in the definition of SAE refers to an event in which the participant was at risk of death at the time of the event. It does not refer to an event which hypothetically might have caused death if it were more severe.

### 6.4 Suspected Unexpected Serious Adverse Reaction (SUSAR)

A SUSAR is an AR, the nature or severity of which is not consistent with the information on the experiment, and, when a clinical Trial is concerned, with the applicable product information (e.g. Investigator's brochure (IB) for an unauthorised investigational product or the patient leaflet joined to the summary of product characteristics for an authorised product).

 Guideline for good clinical practice E6(R2) Step 5 EMA/CHMP/ICH/135/1995 dated 1 December 2016

 Belgian law of May 7th 2004 regarding experiments on the human person (as amended) or the Belgian law of May 7th 2017 related to clinical trials on medicinal products for human use (as soon as in effect),

 ICH E2A Clinical Safety Data Management: Definitions and Standards for Expedited Reporting CPMP/ICH/377/95 dated Jun 1995

## 6.5 Adverse Events of Special Interest (AESI)

The following events should always be reported within the same timelines as SAEs:

- Overdose
- Misuse/abuse
- Medication error

## 6.6 Safety Events that do not require reporting

In general, the following should not be reported as AEs:

- Pre-existing conditions, including those found as a result of screening (these should be reported as medical history or concomitant illness), unless the condition worsens during Trial treatment

The following AEs are commonly observed and expected, and/or are part of the well-known safety profile of OCALIVA® as documented in the Summary of Product Characteristics (SmPC) when used within the approved indication, and are therefore not considered adverse events for the purpose of the Trial:

- stomach pain
- feeling tired
- thyroid hormone irregularity
- dizziness
- fast or irregular heart beat (palpitations)
- pain in the mouth and throat
- constipation
- itchy, dry and/or red skin (eczema)
- rash
- pain in your joints
- swelling in the hands and feet
- fever

Although these events should not be reported to the Sponsor, these should be recorded in the participant's medical notes according to routine practice.

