### Farnesoid X receptor (FXR) agonist

Farnesoid X receptor (FXR) is a bile acid receptor, which is mainly expressed in the liver and intestine. FXR regulates synthesis, secretion and transport of bile acids (18). It has been considered as a promising target for the treatment of cholestatic disorders, including primary biliary cirrhosis (PBC) (19). FXR is also important for the regulation of the lipid and glucose metabolism (18). The activation of FXR showed beneficial effects on various metabolic diseases, including fatty liver diseases, type 2 diabetes, dyslipidemia, and obesity (18). Obeticholic acid (OCA), a FXR agonist, is proven as an effective drug for PBC (19). In 2016, OCA was approved in U.S. and Europe for the treatment of PBC. OCA is used together with another

medicine, ursodeoxycholic acid (UDCA), in patients who do not respond sufficiently to UDCA alone, and on its own in patients who cannot take UDCA. Now, phase III study for NASH is ongoing. In healthy volunteers, patients with primary biliary cholangitis (PBC) and patients with non-alcoholic steatohepatitis (NASH), single and multiple doses of obeticholic acid were well tolerated (19, 20). The most frequently reported adverse events considered to be drug-related were pruritus and fatigue (19, 20). Some abdominal pain and discomfort were reported. Based on a multiple-center phase III study in PBC patients, the recommended starting dosage of OCA is 5 mg orally once daily for 3 months with titration to 10 mg once daily based upon tolerability and response(21). In conclusion, obeticholic acid was found to be safe.

Recently, Friedman ES et al showed alteration of gut microbiome by OCA. In this study, male C57BL/6 mice were gavaged daily with water, vehicle, or OCA (10 mg/kg) for 2 weeks. Small intestine luminal contents were collected by flushing with saline and fecal pellets were collected at baseline and day 14. Culture experiments were performed to determine taxonomic-specific effects of bile acids and OCA on bacterial growth. As a result, administration of OCA dramatically led lower endogenous bile acid levels and an increased proportion of Firmicutes, specifically in the small intestine but not in stool, compared to control in mice (22). Friedman ES et al also conducted healthy volunteers on OCA doses of 5, 10 or 25mg/d and analyzed their microbiome in stool (22), however it is still unclear how the intestinal microbiome changes in human.

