## 5 Trial Medication / Drug

Generic Drug Name (& company brand name)	IMP or non-IMP	Used within Indication? (Y or N)	Route of administration (po,sc,iv,...)	Dose/dosage and units
Obeticholic acid (OCALIVA®)	IMP	N	po	10 mg
Placebo	IMP	N	po	placebo

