## 6.7 Recording and Reporting of Safety Events

Investigators will seek information on the occurrence of safety events at each participant contact. All events, whether reported by the participant or noted by Trial staff, will be recorded in a timely manner in the participant's medical record and in the (e)CRF. If available, the *diagnosis* should be reported on the appropriate (S)AE page in the (e)CRF, rather than the individual signs or symptoms. If no diagnosis is available, the Investigator should record each sign and symptom as individual safety events.

The following minimum information should be recorded for each event:

- event description
- start and stop date of the event
- severity
- seriousness
- causality assessment to the IMP and/or Trial procedures
- outcome

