### 6.8 Reporting requirements to Ethics Committees (ECs) and Competent Authorities (CAs)

The Investigator is responsible for ensuring that all safety events are recorded in the (e)CRF and reported to the Sponsor in accordance with instructions provided in the protocol.

The Sponsor will promptly evaluate all SAEs and AESIs against medical experience to identify and expeditiously communicate possible new safety findings to Investigators, EC(s) and applicable CA(s) and participants as appropriate, in accordance with applicable legislation.

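### Section 6.6 removes 12 known side effects of obeticholic acid from adverse event status, while section 6.7 requires every event in the (e)CRF; the two must be reconciled

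*Combined protocol and SAP*

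**What the plan says.** Section 6.6 lists 12 event types, among them stomach pain, tiredness, rash and fever. It places them in the drug's known profile "when used within the approved indication, and are therefore not considered adverse events for the purpose of the Trial", and closes: "Although these events should not be reported to the Sponsor, these should be recorded in the participant's medical notes according to routine practice".

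Section 6.7 sets the general recording rule. All events, whether the participant or the staff notice them, "will be recorded in a timely manner in the participant's medical record and in the (e)CRF". It adds: "If no diagnosis is available, the Investigator should record each sign and symptom as individual safety events".

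Section 6.8 makes the Investigator responsible for "ensuring that all safety events are recorded in the (e)CRF and reported to the Sponsor", subject to the protocol's own instructions. The overview table in 6.8.3 likewise leaves the timing of AE reports to the protocol.

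Section 6.1 defines an adverse event broadly, with no exclusion for expected events: "An AE can therefore be any unfavourable and unintended sign (including an abnormal laboratory finding), symptom or disease temporally associated".

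On what to expect from the drug, the background section says: "The most frequently reported adverse events considered to be drug-related were pruritus and fatigue". The appendix gives a longer list of possible side effects.

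**The concern.** A participant who reports tiredness in week two has, under 6.6, no adverse event and needs only a line in the medical notes. Under 6.7 the same complaint is a safety event to be entered in the (e)CRF. Staff could follow either section in good faith, and two participants with the same symptom could be recorded differently.

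The events at issue are the ones where a difference between obeticholic acid and placebo would be most expected. In a placebo-controlled crossover, the placebo period is what separates a drug effect from background complaints or from the effects of endoscopy and catheter placement. If the listed events stay out of the (e)CRF, that separation cannot be made from the trial database for most of the drug's known effects.

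**Working it through.** There is no plan figure to reproduce. The check is a count and a side-by-side reading.

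**1. How much of the known profile 6.6 covers.** The appendix lists pruritus (1), two further effects under its very common heading (2) and ten under its common heading (10): 1 + 2 + 10 = 13. The 6.6 list has 12 entries, and all 12 are in the appendix list. The overlap is therefore 12 of 13, with only pruritus as such left out. Of the two most frequent drug-related events named in the background, one (fatigue) is on the 6.6 list and one (pruritus) is not. No event rate is estimated here.

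**2. Where a listed, non-serious event goes.**
- 6.6: it is not an adverse event and is not reported to the Sponsor. It goes in the medical notes. The section does not mention the (e)CRF, but an event that is not an adverse event has no place on the AE form.
- 6.7: it goes in the medical record and the (e)CRF, as an individual sign or symptom if there is no diagnosis. There is no cross-reference to 6.6.
- 6.7.1: all safety events are evaluated for seriousness, severity and causality. Again there is no exception.

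**3. Whether the qualifiers resolve it.** The qualifiers in 6.8 and 6.8.3 can be read as letting 6.6 act as an exception to Sponsor reporting. Neither says that a listed event may be left out of the (e)CRF. Section 6.6 itself is headed as dealing with safety events, so taking away the adverse event label does not clearly take an event out of 6.7, which covers all events.

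**4. Limits on the exclusion.** Section 6.6 sets none by cause. Stomach pain, fever and throat pain could follow endoscopy or catheter placement, and the appendix names sore throat as a catheter risk. Nor does it set one by seriousness. Section 6.7.2 requires all SAEs to reach the Sponsor within 24 hours, while the SAE row of 6.8.3 allows exceptions defined in the protocol. Section 6.6 does not say whether it is such an exception.

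**5. What source notes would contain.** Section 6.7 asks for description, start and stop dates, severity, seriousness, causality and outcome. Notes kept under routine practice need not hold all of these, and without a start date an event cannot be assigned to a treatment period.

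**6. A minor point, separate from the above.** Section 6.7.2 ends AE reporting at 30 days after the last dose or at the last follow-up visit, whichever is first. That visit is not defined. From the flowchart footnote on study drug, the last dose falls at about day 21 + 28 + 21 = 70, and 30 days later is day 100. Depending on which visit is meant, and whether it closes the window, post-dose capture could be anywhere from 0 to 30 days.

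**The case against.** The best defence is that 6.6 is the specific rule and 6.7 and 6.8 are the general ones, so the specific rule governs. For Sponsor reporting this is a fair reading. A reader might infer a flat contradiction there too, but the qualifiers in 6.8 and 6.8.3 do not support that. For (e)CRF recording the defence is incomplete, because 6.6 is silent on the (e)CRF and 6.7 makes no exception.

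Second, the plan makes no safety comparison that this could spoil. Safety is neither an objective nor an endpoint, and section 7 describes no adverse event analysis. That stands, and it limits the importance of the point.

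Third, the events are not lost. They remain in the medical notes, there are only 12 participants, and the coordinating investigator holds both Investigator and Sponsor responsibilities, so a return to source is feasible. Abdominal pain and cramps are also scored on visual analogue scales during the motility and drinking tests. This is true, but the scales cover test days only and routine notes need not carry the 6.7 data items.

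Fourth, a cross-reference from 6.7 to 6.6 would remove the contradiction with less change. It would, but it would settle the matter by leaving most of the known side effects out of the AE data.

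**Conclusion.** The conflict over (e)CRF recording is in the current text and should be fixed. If 6.6 is followed, 12 of the 13 drug side effects in the appendix are absent from the (e)CRF AE data; if 6.7 is followed, none is absent for this reason. The conclusion rests on reading 6.6 as removing the listed events from the AE form, and on section 7 as supplied. The primary hunger/appetite comparison is not affected.

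Four stronger readings are tempting but not supported:
- **Serious events escape reporting.** Section 6.7.2 covers all SAEs, so serious cases appear to remain reportable. What is missing is an explicit statement.
- **6.6 fails because the drug is used outside its indication here.** The section 5 table does mark the use as outside indication. But 6.6 joins its grounds with and/or, so the ground that the events are common and expected can stand alone.
- **Post-dose capture is nil.** That requires treating the day 66 to 70 visit, which the flowchart places in the treatment period, as the last follow-up visit. The flowchart table is also damaged in the text available. Only the lack of a definition is established.
- **Deaths are exempted.** Section 6.7.6 excepts deaths defined under 6.6, but 6.6 defines none, so the exception has no effect.

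**What to change.** Reconcile 6.6 with 6.1, 6.7 and 6.8:
- Delete the statement in 6.6 that the listed events are not adverse events.
- State that they are recorded on the existing (e)CRF AE form with the 6.7 data items, so that they can be listed by treatment at onset.
- If an exemption from Sponsor reporting is kept, say that it covers non-serious events only.

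As a separate clarification, define the last follow-up visit in 6.7.2.

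The cost is protocol wording and a few extra form entries for 12 participants. The number of entries is not estimated. No visit or procedure is added.
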